12.6.2 Analysis of Primary Endpoints

12.6.2.1 Safety

SAEs and non-SAEs will be summarized by descriptive statistics.

12.6.2.2 Intratumoral Immune Infiltration

For all subjects, immune cell subsets and localization will be summarized by changes from baseline to after treatment. Patients will be considered to have a positive response if there is ≥ 2 fold decrease in the number of B cells, or considered to have a negative response if there is < 2 fold decrease in the number of B cells. The proportion of patients who have “positive” responses will be reported, with 95% confidence intervals. Descriptive statistics will be used to describe pre-treatment biopsy immune infiltration, post-treatment RP immune infiltration, and immune infiltration of reference RP tissue.

12.6.3 Analysis of Secondary Endpoints

12.6.3.1 Circulating immune subsets

For each patient, flow cytometry of circulating immune cell subsets will also be performed on pre-treatment blood and again after RP. Established flow

cytometry panels will examine B cell and T cell populations. Immune cell quantification will be summarized by changes from baseline to after treatment using descriptive statistics. Furthermore, paired Wilcox on signed-rank test will be applied to test the pre-post treatment changes. When available, immune cells digested from resected tumor tissues will also be assessed by flow cytometry.

12.6.3.2 Cytotoxic effects and clinical benefits: rate of downstaging, pT0 rate, $\geq 50\%$ PSA decline (phase II)

Point estimates and 95% confidence intervals of pathologic T0 rate at the time of RP will be obtained for phase 2 subjects treated with ibrutinib. Pathologic T0 rate at the time of RP will be compared with the null hypothesis rate separately by using binomial test.

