2.1.2 Secondary Objectives

1. To characterize changes in the frequency and number of circulating B and T cells induced by neoadjuvant ibrutinib in patients with localized prostate cancer.
2. To determine the cytotoxic effect and clinical benefit of neoadjuvant ibrutinib in men with localized prostate cancer.

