6.1.3 Other Modalities or Procedures

Blood samples for PSA and for immune assays will be collected at baseline, before RP, and after RP. Radical prostatectomy will be performed at Washington University, at least 7 days but not more than 12 days following the last scheduled dose of ibrutinib (Day 36 to 41; See Table 6.1). Information including WBC count prior to surgery, amount of blood loss during surgery and/or any post-operative complication(s) will be included in the safety analysis. As there is a potential for loss of immune cell infiltration within the prostate tissue after >12 days of not receiving ibrutinib, any patient who undergoes RP after 12 days from the last dose of ibrutinib will be included in the final analysis; however, an additional patient will be accrued as replacement. This will keep the treatment uniform in order to

evaluate for immune response. The maximum number of allowed replacement patients is 4.

Standard institutional practices for the care and treatment of surgical patients will be followed before, during, and after each patient's RP. Patients will be informed in the written consent that radical prostatectomy may be delayed due to adverse events resulting from study treatment, at the discretion of the investigator and performing surgeon.

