8.1.2 Treatment Period

8.1.2.1 Study Procedures, Week 1, Day 1

- Physical examination
- Vital signs

- ECOG performance status
- Evaluation of adverse events
- Concomitant medications
- CBC with differential and platelet count
- Blood chemistry assessment, including alkaline phosphatase, AST, ALT, total bilirubin, calcium, phosphorus, BUN, creatinine, total protein, albumin, glucose, potassium, sodium, chloride, bicarbonate, LDH
- PSA

8.1.2.2 Study Procedures, Week 2, Day 8

- Telephone Visit
 - Evaluation of adverse events
 - Concomitant medications
 - Other pertinent interval history
- CBC with differential and platelet count (not required to be completed at Washington University, but results must be communicated to the CRC within protocol window)

8.1.2.3 Study Procedures, Week 3, Day 15

- Physical examination
- Vital signs
- ECOG performance status
- Evaluation of adverse events
- Concomitant medications
- CBC with differential and platelet count
- Blood chemistry assessment, including alkaline phosphatase, AST, ALT, total bilirubin, calcium, phosphorus, BUN, creatinine, total protein, albumin, glucose, potassium, sodium, chloride, bicarbonate, LDH

8.1.2.4 Study Procedures, Week 4, Day 22

- Telephone visit
 - Evaluation of adverse events
 - Concomitant medications
 - Other pertinent interval history
- CBC with differential and platelet count (not required to be completed at Washington University, but results must be communicated to the CRC within protocol window)

8.1.2.5 Study Procedures, Week 5, Day 29

- Physical examination
- Vital signs
- ECOG performance status
- Evaluation of adverse events

- Concomitant medications
- CBC with differential and platelet count
- Blood chemistry assessment, including alkaline phosphatase, AST, ALT, total bilirubin, calcium, phosphorus, BUN, creatinine, total protein, albumin, glucose, potassium, sodium, chloride, bicarbonate, LDH
- PSA
- Serum collection in eight 10mL EDTA tubes for immune monitoring to be sent to the TPC at Washington University

RP will be performed 7 to 12 days after the last dose of ibrutinib (between Week 6, Day 36 and Day 41).

8.1.3 Post-RP/Follow Up Visit (Week 10, Day 64):

Patients will be followed approximately 4 weeks after RP. The following procedures will be performed at the follow up Visit:

- Physical examination
- Vital signs
- ECOG performance status
- Evaluation of adverse events
- Concomitant medications
- CBC with differential and platelet count

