9 REPORTING AND DOCUMENTATION OF RESULTS

9.1 Evaluation of Activity

9.1.1 Characterization of PBMCs using flow cytometry

The number and frequency of immune cell subsets in the peripheral blood, before, during and after ibrutinib therapy will be assessed. Fluorochrome-labeled antihuman antibodies, including antibodies to CD19, CD25, CD27, CD86, CD3, CD8, CD4, CD25, and FOXP3 will be used. Flow cytometry will be performed in either the Immunomonitoring Lab (IML) or [name] Lab in the Center for Human Immunology and Immunotherapy Programs (CHiiPs) at Washington University.

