11 DATA SUBMISSION SCHEDULE

Case report forms with appropriate source documentation will be completed according to the schedule listed in this section.

Case Report Form	Submission Schedule
Original Consent Form	Prior to registration
On-Study Form Medical and Surgical History	Prior to starting treatment
Concomitant Medications Form Toxicity Form	Continuous
PSA Form	Baseline, Week 1, Week 5, Post-RP Follow-Up Visit
Research Blood Form	Baseline, Week 5, Post-RP Follow-Up Visit
Treatment Summary Form	Completion of treatment
RP Form	Time of surgery
Progression Form	Time of disease progression
MedWatch Form	See Section 7.0 for reporting requirements
Death Form	At time of death

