APPENDIX 3: SPECIMEN COLLECTION

A: For tissue analyses:

Paired pre- and post- treatment tumor tissue specimens will be collected in all patients and analysis will be performed per section 8. Specimens will be processed initially through the Tissue Procurement Core Facility.

B: For blood analyses:

All patients will have 8 (eight) 10mL tubes of blood specimens collected at baseline, at the end of ibrutinib therapy, and after RP. The collection will be divided into 60 mL in 6 EDTA tubes for PBMCs for immune monitoring and 20 mL in 2 EDTA tubes for plasma for cytokines.:.

These specimens will be transported at room temperature to the Tissue Procurement Core Facility where they will be processed using their SOPs to obtain plasma and PBMCs.

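### The test of ibrutinib's effect on circulating B and T cells compares baseline with blood drawn after prostatectomy, while the pre-surgery end-of-therapy sample has no stated analysis

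*Combined protocol and SAP*

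**What the plan says.** The first secondary objective (2.1.2) reads: "To characterize changes in the frequency and number of circulating B and T cells induced by neoadjuvant ibrutinib". The matching endpoint in 2.2.2 classifies patients by a 2-fold decrease from pre-treatment to post-treatment, without naming the post-treatment visit.

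The analysis is in 12.6.3.1. It states that "flow cytometry of circulating immune cell subsets will also be performed on pre-treatment blood and again after RP", summarises change from baseline to after treatment, and adds that a paired "signed-rank test will be applied to test the pre-post treatment changes". It gives no visit, significance level or sidedness for the test. The only two blood samples it mentions are the pre-treatment and post-RP ones.

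The collection sections all give three immune samples:
- 6.1.3: blood "for immune assays will be collected at baseline, before RP, and after RP".
- 8.1.2.5 (Week 5, Day 29): "Serum collection in eight 10mL EDTA tubes for immune monitoring to be sent to the TPC". The table in 8.2 marks immune monitoring at screening, Week 5 and the post-RP visit.
- Section 11, Research Blood Form: "Baseline, Week 5, Post-RP Follow-Up Visit".
- Appendix 3: tubes "collected at baseline, at the end of ibrutinib therapy, and after RP".

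Section 9.1.1 says that peripheral blood subsets "before, during and after ibrutinib therapy will be assessed". That covers the Week 5 sample but specifies no contrast.

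**The concern.** The objective asks what ibrutinib does to circulating lymphocytes. The sample best placed to answer is the one drawn at the end of therapy and before surgery. The analysis section passes over it and names the sample drawn after a major operation and about five weeks off drug.

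A change at that later visit can have several sources: what remains of the drug effect, loss of effect during washout, recovery from prostatectomy, and hormone or radiation therapy, which 8.5 permits after RP. The plan has no means of separating these. Under 12.7 the 12 reference patients are described as contributing RP specimens, so they supply no blood comparison.

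The error could go either way. A change present at the end of therapy could have faded by the post-RP visit and be missed, or a change caused by surgery could be credited to ibrutinib.

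**Working it through.** The plan states no power or significance level for this test, so there is no figure of its own to reproduce. The check is day arithmetic, followed by an illustration on assumed effect sizes.

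**Inputs.** Dosing on Days 1-28 (6.1.2). RP 7 to 12 days after the last dose, printed as Day 36 to 41 (6.1.3, 8.1.2.5, 8.2). Post-RP visit on Day 64, +/-3 days (8.1.3, 8.2). Week 5 visit on Day 29, +/-3 days (8.2).

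**Time since last dose, 4-week schedule.**
- Week 5 sample: 29 - 28 = 1 day. With the window it falls on Day 26 to 32, at or near the end of dosing and before the earliest planned RP.
- Post-RP sample: 64 - 28 = 36 days; with the window, 61 - 28 = 33 to 67 - 28 = 39.

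**Time since RP at the post-RP sample.** The two statements of RP timing do not agree. Seven to 12 days after Day 28 is Day 35 to 40; the printed Day 36 to 41 is 8 to 13 days after it. These must be reconciled.
- Printed days: 64 - 41 = 23 to 64 - 36 = 28.
- 7-to-12-day rule: 64 - 40 = 24 to 64 - 35 = 29.
- Combined: 23 to 29 days; with the visit window, 61 - 41 = 20 to 67 - 35 = 32.

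Patients whose RP is delayed beyond 12 days stay in the final analysis (12.4). As an example, RP 21 days after the last dose followed by a visit 4 weeks later gives 21 + 28 = 49 days off drug.

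**Patients dosed for 2 weeks.** Three were treated at UCSF, and their data are analysed under this study (3.2, 12.9). The de-escalation levels in 12.5 also last 2 weeks. If the last dose is on Day 14, RP 7 to 12 days later falls on Day 21 to 26. A Day 29 sample would then be 3 to 8 days after surgery. A fix worded as Day 29 would therefore fail for these patients.

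**Illustration only.** Assumed, not in the documents: 24 complete pairs, two-sided 0.05, normally distributed log fold changes, and effect sizes in SD units of the paired change. Exact signed-rank rejection region W <= 81 or W >= 219 (true size 0.049), 200,000 simulated trials per cell.

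| End-of-therapy change | 100% remains at post-RP visit | 75% | 50% | 25% |
|---|---|---|---|---|
| 0.6 SD | 78% | 54% | 28% | 10% |
| 0.8 SD | 96% | 79% | 45% | 15% |

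In the other direction, with no drug effect at all, a shift of 0.3 or 0.5 SD caused by surgery alone gives a significant result in 28% or 63% of trials.

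**The case against.** A reader might infer that the visit is left open and could be picked after the data are seen. With two eligible visits at an assumed 0.05 each, the false-positive chance per subset would be about 0.070 (correlation 0.9) to 0.0975 (independence). The documents do not support that reading. Section 12.6.3.1 names exactly two samples and refers to the pre-post change in the same paragraph, so its plain meaning is pre-treatment against post-RP. Section 9.1.1 does not reopen this: its three time points map one to one onto baseline, Week 5 and post-RP, and it is an assay section that defines no contrast. The valid complaint is that the named contrast does not match the objective, and that 2.2.2 and 9.1.1 do not state the visit.

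A second tempting inference is that the post-RP contrast is known to lose power or to mislead. That is not shown either. Section 5.1.2 describes BTK inhibition as irreversible, and no section says how long circulating subsets stay changed. Nor do the documents say how many patients start hormone or radiation therapy before the post-RP sample. The power figures are generic signed-rank results under assumed inputs.

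Third, there is no blood control at either visit. Moving the contrast before surgery removes the effects of surgery, post-RP therapy and most of the washout. It does not remove other changes over time. This objection stands as a limit on what the fix achieves.

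Finally, no decision rule or sample size depends on this test. That limits the importance of the point without answering it.

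**Conclusion.** The concern holds as a mismatch between objective and analysis. Followed as written, 12.6.3.1 tests change attributed to ibrutinib on a sample nominally 36 days off drug and 23 to 29 days after prostatectomy. A less confounded sample is already collected and has no stated analysis. The timing follows from the schedule for 4-week dosing. The size of any resulting error cannot be determined from the documents: nothing is lost if the drug effect fully persists and surgery causes no shift, and the loss could be large otherwise. The point concerns one secondary endpoint and leaves the primary B-cell endpoint and its sample size untouched. It should be corrected because the remedy is cheap and the present contrast cannot be cleanly attributed to the drug.

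**What to change.** In 12.6.3.1, make baseline against the end-of-therapy sample taken before RP the signed-rank contrast for the drug effect. Define that sample relative to last dose and RP (Week 5 on the 4-week schedule) rather than as Day 29, so that it is pre-surgery for patients dosed for 2 weeks as well. Summarise separately any such patient without a pre-RP sample.

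Report baseline against post-RP as a descriptive summary of persistence and recovery, noting any hormone or radiation therapy begun before that sample. If the sponsor prefers to test the post-RP contrast, the plan should say so and give the reason before data are seen.

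Use the same named visit for the 2-fold responder definition in 2.2.2, and align the wording of 9.1.1. Reconcile the 7-to-12-day interval with the printed Day 36 to 41.

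Cost: no extra blood draws on the 4-week schedule, because the Week 5 tubes are already collected for immune monitoring. At most there is one flow cytometry run per patient, about 24, or 24 + 4 = 28 with the allowed replacements, and none if 9.1.1 already plans them. The rest is a text change.

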12.6.4 Analysis of Exploratory Endpoints

12.6.4.1 Assessment of Btk expression

Btk expression on tumor tissue from pre-treatment biopsies, RP specimens, and any other tumor biospecimens obtained will be evaluated immunohistochemically and graded as low, intermediate or high. Frequency distribution and percentage will be used to summarize Btk expression by pre- and post- treatment. In addition, Kappa statistics will be used to test if there is any change of Btk expression from pre-treatment biopsy to post-treatment RP tissue.

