2.1.3 Exploratory Objectives

1. To examine Btk expression in prostate tumor cells and tumor-infiltrating B cells at baseline before neoadjuvant ibrutinib treatment and at RP after treatment.
2. To determine the impact of neoadjuvant ibrutinib on PD-L1 expression in prostate cancer cells and tumor-infiltrating lymphocytes (TILs).
3. To determine the effects of neoadjuvant ibrutinib on T and B cell repertoire within the tumor and blood.

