12.3 Sample Size and Power Estimate

For this phase 2 study, the primary endpoint is the change of B cells between the pre-treatment biopsy and post-treatment RP specimen. Each patient's response to neoadjuvant ibrutinib will be a binary classification. Patients will be considered to have a

“positive” response if there is >2 fold decrease in the number of B cells, or considered to have a “negative” response if there is <2 fold decrease in the number of B cells. The accrual of 18 patients to the phase 2 trial and incorporation of 6 patients who received ibrutinib at MTD in the safety lead-in (a total of 24 evaluable subjects) will be sufficient to determine whether 20% or more of the cohort achieves this 2 fold decrease in B cells, compared to a null response of 5% or less of a reference group of patients who underwent RP without neoadjuvant treatment. This comparison has a power of 0.818 at a significance level of 0.044 based on a one-sided binomial exact test. If 4 more evaluable patients show a “positive” response, the treatment achieves the expected “response” rate of 20%.

The safety-run in will require 6 patients (with a potential for 6-12 more if dose de-escalation is required). The Phase II study will require a total of 24 patients on MTD and thus 18 additionally enrolled patients besides the 6 on MTD during the safety lead-in.

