12.6.4.2 Assessment of PD-L1 expression

PD-L1 protein expression on tumor tissue from pre-treatment biopsies, RP specimens, and any other tumor biospecimens obtained will be evaluated immunohistochemically and scored on a scale of 0, 1, 2, or 3. We will categorize tumors based on the frequency of tumor cells or of immune cells staining positively for PD-L1 as follows: IHC 0: $<1\%$, IHC 1: $1-5\%$, IHC 2: $5-10\%$ and IHC 3: $\geq 10\%$. Frequency distribution and percentage will be used to summarize PD-L1 protein expression by pre- and post- treatment. Furthermore, McNemar's test will be used to assess the impact of the treatment on PD-L1 expression by considering IHC estimates of $\geq 10\%$ as being positive.

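### Kappa is named as the test of change in Btk grade, but it measures agreement: it neither tests for a systematic shift nor shows direction

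*Combined protocol and SAP*

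**What the plan says.** Section 12.6.4.1 has Btk expression on tumor tissue "evaluated immunohistochemically and graded as low, intermediate or high". It plans a descriptive summary, "Frequency distribution and percentage will be used to summarize Btk expression by pre- and post- treatment", and then adds the inferential step: "Kappa statistics will be used to test if there is any change of Btk expression from pre-treatment biopsy to post-treatment RP tissue".

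The data are paired. Appendix 3 states "Paired pre- and post- treatment tumor tissue specimens will be collected in all patients", and the first exploratory objective in section 2.1.3 looks at Btk "at baseline before neoadjuvant ibrutinib treatment and at RP after treatment". Section 12.3 plans for "a total of 24 evaluable subjects".

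No null value, weighting, significance level or rule for reading kappa is given, and no other test of Btk change appears. For similar paired questions the plan names tests of change. In section 12.6.4.2, McNemar's "test will be used to assess the impact of the treatment on PD-L1 expression"; in section 12.6.3.1, circulating immune subsets get a paired signed-rank test.

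**The concern.** The question is whether an ordered grade moves between two specimens from the same man. Kappa asks whether the two grades match more often than their marginal distributions would produce by chance. Three problems follow.

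- **Null.** The usual test of kappa has chance agreement as its null, so its p-value is smallest when nobody changes.
- **Direction.** Kappa is symmetric in pre and post. A fall and the mirror-image rise give the same value.
- **Systematic versus random.** Kappa drops with disagreement of any kind. A one-way drug effect and random regrading can give the same value, and core biopsy and whole prostatectomy may well differ through sampling alone.

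Btk is the drug's target, so a wrong reading here would matter to how the tissue findings are interpreted. Followed literally, the analysis could report significant agreement as change, or treat a one-way fall as no different from noise.

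**Working it through.** The plan attaches no figure to this analysis, so there is none to reproduce, and it gives no expected Btk distribution. All tables below are therefore assumptions, built on 24 pairs (section 12.3) and three grades (section 12.6.4.1). Rows are pre-treatment and columns post-treatment, in the order low, intermediate, high.

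**Formulas**
- Kappa = (Po − Pe)/(1 − Pe), where Po is the share of men with the same grade twice and Pe = Σ(row total × column total)/24².
- Exact two-sided sign test on the men who change grade; if all m move the same way, p = 2 × 0.5^m.

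**Two tables with the same number of men changing**

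1. Twelve unchanged, twelve fall one grade: [[4,0,0],[6,4,0],[0,6,4]].
 - Row totals 4, 10, 10; column totals 10, 10, 4.
 - Po = 12/24 = 0.500.
 - Pe = (4×10 + 10×10 + 10×4)/576 = 180/576 = 0.3125.
 - Kappa = 0.1875/0.6875 = 0.273.
 - Sign test, 12 against 0: p = 2 × 0.5¹² = 0.0005.
2. Twelve unchanged, six rise, six fall: [[5,3,0],[3,3,3],[0,3,4]].
 - Row and column totals both 8, 9, 7.
 - Po = 0.500.
 - Pe = (64 + 81 + 49)/576 = 194/576 = 0.337.
 - Kappa = 0.163/0.663 = 0.246.
 - Sign test, 6 against 6: p = 1.0.

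The kappas are almost equal; the paired tests point in opposite directions.

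**Further tables, 24 pairs each.** The kappa p-value uses the standard error under kappa = 0.

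| Assumed pattern | Kappa | p for kappa | Linear-weighted kappa | Sign test p | Stuart-Maxwell p |
|---|---|---|---|---|---|
| Nobody changes | 1.00 | <0.0001 | 1.00 | 1.0 (no one moves) | not defined |
| 8 fall one grade, none rise | 0.50 | 0.0003 | 0.625 | 0.008 | 0.018 |
| 8 rise one grade, none fall | 0.50 | 0.0003 | 0.625 | 0.008 | 0.018 |
| 4 rise, 4 fall | 0.50 | 0.0005 | 0.625 | 1.0 | 1.0 |
| 16 fall one grade, none rise | 0.00 | 1.0 | 0.25 | 0.00003 | 0.0003 |

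The tables are, in order: [[8,0,0],[0,8,0],[0,0,8]]; [[8,0,0],[4,4,0],[0,4,4]]; its transpose; [[6,2,0],[2,4,2],[0,2,6]]; and [[8,0,0],[8,0,0],[0,8,0]].

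Rows two to four show that kappa cannot tell a fall from a rise, or either from scatter. Linear weights do not help. The first and last rows show the p-value running the wrong way: smallest when nothing happened, and 1.0 when two thirds of the men fell. In the last row weighted kappa is significant for agreement (p = 0.014) in the same situation.

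**The case against.** The best defense has four parts.

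- **Kappa does respond to change.** It is 1.0 if no grade moves and falls as men are reclassified, and the plan asks about any change without stating a direction. This stands in part: kappa registers disagreement. It does not separate net shift from scatter, and its usual p-value does not test for no change.
- **The same paragraph plans pre and post percentages.** In table 1 these would show 4/10/10 becoming 10/10/4; in table 2, 8/9/7 both times. A reader of the whole paragraph would see the difference. That softens the consequence. But the summary is descriptive, does not show how many individual men moved each way, and leaves the named test unchanged.
- **The result depends on the assumed tables.** True. If all 24 men fall one grade from 12 intermediate and 12 high, Po = 0, Pe = (12×12)/576 = 0.25 and kappa = −0.33, clearly below chance. But if all 24 go from high to intermediate, Po = Pe = 0 and kappa is 0. That the answer hinges on the baseline mix is itself a reason not to use it as a test of change.
- **The endpoint is exploratory.** It has no power, sample size or decision attached. This limits the severity; it does not make the method suitable.

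Two limits apply to any replacement as well. Section 9.1.5 describes Btk staining only on core biopsy taken before surgery, which should be reconciled with sections 2.1.3, 2.2.3 and 12.6.4.1, since without post-treatment staining there are no pairs. And no paired test can separate a drug effect from a biopsy-versus-prostatectomy sampling difference.

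**Conclusion.** The concern holds. As a test of change in Btk grade, kappa is the wrong statistic: its usual null is chance agreement, it has no direction, and it can take the same value for a one-way shift as for symmetric noise. In the two worked tables it gives 0.27 and 0.25 where an exact sign test gives p = 0.0005 and p = 1.0.

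The argument from the null and from symmetry needs no assumed data. The sizes do: they rest on illustrative tables, on all 24 pairs being available (tissue sufficiency is not an eligibility requirement in section 3.3.1, so fewer are likely), and on the standard null of kappa = 0, because the plan states none. The primary endpoint and sample size are untouched. The point should be corrected, but it is not critical to the trial.

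**What to change.** In section 12.6.4.1, replace the kappa sentence with one that:

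- tests change in the ordered grade (low = 1, intermediate = 2, high = 3) with a two-sided Wilcoxon signed-rank test in its exact form, which treats one-grade steps as equally spaced; or, to avoid that spacing, with a Stuart-Maxwell test of marginal homogeneity;
- reports the full 3×3 pre/post table, with the numbers of men whose grade rose, fell or stayed the same, and the number without an evaluable pair;
- keeps kappa, if wanted, only as a descriptive agreement measure, stating whether it is weighted.

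Choose one test now, before any Btk readings are seen. This brings Btk into line with the paired tests already planned for PD-L1 and circulating cells. The cost is one sentence in the plan: no extra patients, and no tissue beyond the pairs the plan already calls for.
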